6.3 Baseline Visit

Subjects who meet eligibility criteria will return for a baseline visit. This visit will include the following procedures and will take place over several days:

- Repeat review of informed consent
- Review of inclusion/exclusion criteria
- Medical and allergy history
- Concomitant medications
- Physical examination, including weight and height
- Vital signs (blood pressure, pulse rate, body temperature)
- Spirometry (FEV1) and/or PEFR prior to any DBPCFC; 3 attempts of FEV1 are performed, and the best value is taken; 3 attempts of PEFR are to be performed, and the best value taken. PEFR should be measured at the same time for each visit assessment.
- Urine pregnancy test, for females of childbearing potential
- Optional blood draw (pre- and 5-10 days post-DBPCFC) for exploratory analysis by ITN. The amount taken should be 5 mL/kg in children weighing ≥30 kg, with a maximum of 60 mL in total. Blood draw should be completed per National Institutes for Health (NIH) guidelines.
- Physician global assessment of disease activity using a 100-mm VAS

6.4 Study Treatment Visits

6.4.1 Initial Escalation Days 1 to 3 (Visit 01)

The following assessments will be performed at Visit 01 at the Clinical Research Center:

Day 1 Initial Escalation

- OIT administration of peanut protein or matching placebo on escalation day (Visit 01) with dosing beginning at 0.5 mg, with graduated doses up to 6.0 mg (if tolerated). Subjects at the end of Day 1 tolerating less than 3.0 mg single dose will be considered an initial day escalation failure. The schedule for initial day dose escalation is shown in **Table 3-1**.
- Concomitant medications
- Physical examination, including weight and height
- Vital signs (blood pressure, pulse rate, body temperature)
- PEFR (3 attempts are to be performed, and the best value taken). PEFR should be measured at the same time for each visit assessment.

- Diet history
- Monitoring for allergic symptoms (see Section 6.8)
- Adverse events monitoring

Subjects may have clear liquids or JELL-O during the day of the initial day escalation protocol while they are being given the desensitization doses.

If symptoms occur which prevent escalation to 6.0 mg, the highest tolerated dose (at least 3.0 mg) will be accepted as the "desensitization" dose for further escalation (see **Figure 6**–1 in **Section 6.8.4**). The maximum tolerated dose on Day 1 (e.g., 3.0 or 6.0 mg) will be given on Day 2 as a single dose under medical observation at the Clinical Research Center. If moderate symptoms occur on Day 2, the subject will return to the Clinical Research Center on Day 3 for the next lower dose (must be at least 3.0 mg) under direct observation. If symptoms prevent initial escalation desensitization dosing to 3.0 mg, the subject will be dropped from study treatment due to escalation failure and followed longitudinally for safety. These subjects will be asked to return to the Clinical Research Center 14 days following their last dose of study product to undergo an Early Discontinuation Visit (see Section 6.5).

A physician will be available at all times during any of the Clinical Research Center peanut OIT dosing visits.

Day 2 Initial Escalation

All subjects will return to the clinic on Day 2 for their next dose. This dose will be the previous day's dose or the last tolerated dose from the initial day escalation. The maximum dose is 6.0 mg. The minimum dose for Day 2 is 3.0 mg.

Those subjects administered: 3.0 mg

- If tolerated, return home on that dose for 2 weeks until the next escalation
- If not tolerated, the subject is considered an escalation failure, discontinued from treatment, and followed for safety until the Early Discontinuation Visit

Those subjects administered: 6.0 mg

- If tolerated, return home on that dose for 2 weeks until next escalation
- If not tolerated, return on Day 3 with a 1-step reduction (3.0 mg)

Day 3 Initial Escalation

Those subjects with moderate symptoms on Day 2 at the 6.0 mg dose will return on Day 3 for an observed dose. The maximum dose on Day 3 would be 3.0 mg. Those subjects administered 3.0 mg

- If tolerated, return home on that dose for 2 weeks until next escalation.
- If not tolerated, the subject is considered an escalation failure, discontinued from treatment, and followed for safety until the Early Discontinuation Visit.

5 to 10 days post-DBPCFC

• Optional post DBPCFC blood draw for exploratory analysis by ITN. The amount taken should be 5 mL/kg in children weighing ≥30 kg, with a maximum of 60 mL in total. Blood draws should be completed per NIH guidelines.

6.4.2 Up-dosing/Escalation visits (Up to 34 weeks post-Visit 01)

The following procedures are scheduled for the up-dosing phase, which will last approximately 24 weeks).

- Return to clinic every 2 weeks for up-dosing up to a maximum of 300 mg daily dose. The first dose of study product will be administered at the clinic.
- Concomitant medications
- Physical exam, including weight and height
- Vital signs (blood pressure, pulse rate, body temperature)
- PEFR (3 attempts are to be performed, and the best value taken). PEFR should be measured at the same time for each visit assessment.
- Return unused capsules to the clinic at each visit
- Take home capsules for daily dosing until next visit
- Monitoring for compliance and allergic symptoms (phone contact 1 week after each escalation visit)
- Adverse events monitoring

Subjects should not take their daily maintenance dose on the day of the clinic visits. The initial up-dose is to be administered at the clinic.

Subjects who require dosing reduction during the 2-week period will reset their 2-week escalation schedule to maintain the new dose for a 2-week period prior to attempting to escalate again. The procedure for setting the new, lower, dose is outlined in Section 6.8.2 and depends on the severity of the dose-related symptoms. Any dose escalation attempts may be postponed for 1-2 extra weeks based on clinical judgment. An escalation attempt must be made by 4 weeks, unless escalation is to be delayed further due to administration of epinephrine as defined in Section 6.8. Failure to successfully escalate for three consecutive attempts will result in the subject being considered an escalation failure and dose escalation will be halted at the last tolerated dose level. These subjects will be followed for safety biweekly (following their established visit schedule) while continuing to be dosed at their last tolerated dose level until Week 24, i.e., a maintenance phase (see also Section 6.8.4). Dosing will be stopped after the Week 24 visit; and the subject will be asked to return to the Clinical Research Center 14 days following their last dose of study product to undergo an Early Discontinuation Visit (see Section 6.5). For subjects who halt dose-escalation after Week 24, there will be no maintenance phase. Dosing in these subjects will be discontinued when dose-escalation is stopped. They will be asked to return to the Clinical Research Center 14 days

following their last dose of study product to undergo an Early Discontinuation Visit (see **Section 6.5**).

For any noted symptoms during the maintenance phase, the same study dosing rules for build-up phase will be followed. As noted above, for subjects who halt dose-escalation prior to Week 24, the maintenance phase extends to Week 24; and for subjects who halt dose-escalation after Week 24, there is no maintenance phase. For subjects who achieve a dose of 300 mg/d by Week 34, the maintenance phase comprises the last two weeks of the study.

Subjects will continue to follow a peanut restricted diet for the duration of the study.

Note that all study products to be used in the build-up phase for this study have been filled from a single lot, so no reductions based on lot changes should be necessary.

6.4.3 Visit 02 (after approx. 12 weeks post-Visit 01)

- Study product administration at clinic
- Medical/allergy history
- Concomitant medications
- Physical exam, including weight and height
- Vital signs (blood pressure, pulse rate, body temperature)
- PEFR (3 attempts are to be performed, and the best value taken). PEFR should be measured at the same time for each visit assessment.
- Urine pregnancy test, for females of childbearing potential
- Diet history
- Return unused capsules to the clinic at each visit
- Take home capsules for daily dosing until the next visit
- Monitoring for compliance and allergic symptoms (phone contact 1 week after each escalation visit)
- Adverse events monitoring

Subjects will continue to follow a peanut-restricted diet for the duration of the study. For any noted symptoms during the maintenance phase, the same study dosing rules for the build-up phase will be followed.

6.5 Visit 03 - Exit Visit / Early Discontinuation Visit

Subjects who tolerate 300 mg/day and are maintained at this dose for 2 weeks will return to the clinic for an Exit visit. For these subjects, the Exit visit will occur at approximately 6-9 months post-Visit 01.
Subjects who fail escalation or build-up, or who prematurely discontinue treatment, will return to the site for an Early Discontinuation visit that consists of the same procedures as the Exit visit, but without a DBPCFC or associated optional blood draws. An Early Discontinuation visit is to occur 14 days from the last dose of study product.

The following procedures will be performed at the Exit visit:

- Medical/allergy history
- Concomitant medications
- Physical exam, including weight and height
- Vital signs (blood pressure, pulse rate, body temperature)
- PEFR (3 attempts are to be performed, and the best value taken). PEFR should be measured at the same time for each visit assessment.
- Urine pregnancy test, for females of childbearing potential
- Diet history
- Blood draw for peanut-specific IgE and IgG4 measurement (mechanistic assays), the amount to be specified by local laboratory guidelines.
- Optional blood draw (pre-DBPCFC) for exploratory analysis by ITN. The amount taken should be 5 mL/kg in children weighing ≥30 kg, with a maximum of 60 mL in total. Blood draw should be collected per NIH guidelines.
- Skin prick test to peanut extract
- Physician global assessment of disease activity using a 100-mm VAS
- Monitoring for compliance and allergic symptoms

In addition to the procedures listed above, eligible subjects will have an exit DBPCFC performed. Eligible subjects are those who tolerate 300 mg/day and are maintained at this dose for 2 weeks.

For placebo subjects only:

• Exit DBPCFC conducted in accordance with PRACTALL guidelines as described in Section 6.6.2, then proceed to ARC002

For active-treatment subjects completing DBPCFC only:

• Proceed to ARC002

Each subject participating in the study will be unblinded when he/she completes the Exit visit procedures (including the exit DBPCFC for eligible subjects).

6.6 Double-Blind, Placebo Controlled Food Challenge (DBPCFC) in accordance with PRACTALL guidelines

The DBPCFC is performed by feeding gradually increasing amounts of the suspected food under physician observation.^{25,26} A sample of food challenge from the PRACTALL guidelines using peanut flour is given in Table 6-1.

Challenge Doses				
Peanut protein (mg)	Peanut flour with 50% protein content (mg)			
3	6			
10	20			
30	60			
100	200			

Table 6-1. PRACTALL DBPCFC Doses Using Peanut Flour with 50% Peanut Protein Content for Screening DBPCFC

6.6.1 Screening Double-Blind, Placebo Controlled Food Challenge (DBPCFC) – For All Subjects

The initial DBPCFC for eligibility will consist of ascending levels of the peanut flour (containing ~50% peanut protein) or placebo in gradually increasing doses at 20-30 min intervals. The DBPCFC will be performed in accordance with PRACTALL guidelines, but requiring progression in an unaltered sequence without repeating any dose. The procedure will also be modified in that the top dose will be capped at 100 mg (143 mg cumulative) peanut protein or placebo. The PRACTALL doses as shown in **Table 6-1** will be used, as well as PRACTALL rules for safety, assessment, scoring, and stopping. At the investigator's discretion, a 1 mg dose may be added at the beginning of the escalation (for a maximum cumulative dose of 144 mg peanut protein). In the event that the 1 mg dose is added, any rules that apply to subjects based on a cumulative dose of 144 mg.

The DBPCFC is conducted as 2 challenges during a single day visit or over 2 days, using a placebo (oat flour) for one challenge and peanut (as peanut flour) for the other. If conducted in a single day, at least 3 h must separate the first half of the challenge from the second half of the challenge. The challenge is performed under double-blind conditions so that neither the subject, nor the subject's caregiver nor the physician knows which challenge contains the peanut or the placebo.

6.6.2 Exit Double-Blind, Placebo Controlled Food Challenge (DBPCFC)- For All Subjects

The exit DBPCFC will be conducted in a manner similar to the screening DBPCFC but with a dose increasing up to 600 mg (1043 mg cumulative) peanut protein as shown in **Table 6-2**.

Subjects receiving active treatment will be considered a study success if they are able to complete a challenge with 300 mg (443 mg cumulative) peanut protein.

Challenge Doses				
Peanut protein	Peanut flour with 50% protein content			
(mg)	(mg)			
3	6			
10	20			
30	60			
100	200			
300	600			
600	1200			

Table 6-2.	Doses Using Peanut Flour with 50% Peanut Protein Content for Exit
	DBPCFC

6.7 Physician Global Assessment

A 100-mm visual analog scale (VAS) will be used by the investigators to assess overall disease activity as a marker for safety.

In assessing overall disease activity, the investigator should consider the frequency of allergic reactions (both observed and reported), their type, their severity, and the dose level at which they have occurred. With these factors in mind, the investigator is to assign a single integrated overall disease activity score.

The investigators will be asked:

"How would you rate the severity of the overall disease activity on a scale of 0, no disease activity, to 100, very severe disease activity?"

Investigators are permitted to refer back to previous assessments when making their VAS determination of overall disease activity.

Although not validated specifically as an instrument for evaluating food allergies, the VAS is, nevertheless, a widely used tool in assessing disease activity, especially in inflammatory diseases.

6.8 Reactions and Treatment of Reactions

6.8.1 Reactions and Treatment of Reactions to Peanut OIT During Initial Escalation

The process algorithm for symptoms during the initial escalation protocol is shown in **Figure 6–1** in **Section 6.8.4**.

Subjects may develop symptoms during the initial escalation protocol, similar to those seen during other desensitization protocols (e.g., venom immunotherapy, drug desensitization). The severity of the reaction will be determined on the basis of the investigator's judgment, using the definitions in the PRACTALL consensus report on DBPCFC as a general guide. The investigator's judgment will also be required to determine the best course of action, with possible actions being the following:

- Extension of time interval between dosing (up to an additional 30 min) without any additional treatment
- Institution of enhanced clinical monitoring. This could include (though is not limited to) more frequent vital sign monitoring (including respiratory rate), auscultation, and/or the addition of pulse oximetry
- Treating with antihistamine and then resuming dose escalation within 60 min of last dose, if assessed as safe
- Treating additionally with epinephrine, beta-agonist, oxygen, IV fluids, and/or glucocorticosteroids, and discontinuing dose-escalation
- Discontinuation of desensitization protocol

For *oral/pharyngeal pruritus* occurring in isolation – the recommended action is to continue the normal dosing in 30 min (though the action taken is, as always, at the investigator's clinical discretion).

For *mild symptoms*, including, but not limited to:

- Skin limited (few) or localized hives, swelling (e.g., mild lip edema), skin flushing (e.g., few areas of faint erythema) or pruritus (mild, e.g., causing occasional scratching
- Respiratory rhinorrhea (e.g., occasional sniffling or sneezing), nasal congestion, occasional cough, throat discomfort
- Gastrointestinal (GI) mild abdominal discomfort (including mild nausea), minor vomiting (typically a single episode) and/or a single episode of diarrhea

Depending on the investigator's discretion, the action should be either:

- Advance to next dose in 30–60 min or
- Treat with antihistamine and then resume dose escalation within 60 min of last dose, if symptoms have resolved to the point where the investigator assesses the subject as safe to continue dosing (i.e., having no or minimal residual signs or symptoms)

If moderate symptoms occur, including, but not limited to:

- Skin systemic hives (e.g., numerous or widespread hives), swelling (e.g., significant lip or face edema), pruritus causing protracted scratching, more than a few areas of erythema or pronounced erythema
- Respiratory throat tightness without hoarseness, persistent cough, wheezing without dyspnea

• GI – persistent moderate abdominal pain/cramping/nausea, more than a single episode of vomiting and/or diarrhea

If the symptoms are not worsening or amassing at a rapid pace, then a stepwise approach to treatment may be taken at the discretion of the investigator. If the first action undertaken is to implement an observation period, the observation period should not exceed 30 min before either the symptoms are noted to be resolving or therapy is instituted. Whether treatment is initiated immediately or after an observation period, the subject may be treated first with antihistamines or immediately with epinephrine, as deemed appropriate by the investigator. Other therapies may be added either sequentially or simultaneously, per investigator judgment.

If moderate symptoms occur at any of the doses below 6 mg (i.e., up to and including 3 mg), then the desensitization protocol will be discontinued and the subject considered an escalation failure. The decision to discontinue escalation (at any dose below, or at, 3 mg) is based solely on the determination that the symptoms of allergic reaction are moderate, regardless of whether treatment is instituted or what type of treatment is instituted. If moderate symptoms occur only at the 6 mg dose, then the following day's dose (Day 2 or Day 3) will be reduced to 3 mg.

The Medical Monitor is to be available at all times to answer any questions or to assist in any decisions related to the study protocol.

If more *severe symptoms* occur, including, but not limited to:

- Skin severe generalized urticarial/angioedema/erythema
- Respiratory laryngeal edema, throat tightness with hoarseness, wheezing with dyspnea, stridor
- GI significant severe abdominal pain/cramping/repetitive vomiting and/or diarrhea
- Neurological change in mental status
- Circulatory clinically significant hypotension (see Appendix 3)

The actions taken should be to discontinue the initial escalation and administer the appropriate rescue medications. The desensitization protocol will be discontinued regardless of the dose at which the severe symptom or symptoms occurred, and the subject considered an escalation failure.

Summary of Initial Escalation Dosing Requirements (see also Figure 6–1 in Section 6.8.4)

In general, if the subject requires one or two doses of antihistamine treatment for mild symptoms during the initial escalation protocol, then the initial escalation may be continued. If, however, the subject requires a second medication (e.g., epinephrine, a beta-agonist, or other medications) in addition to an antihistamine, or multiple doses of antihistamines, the initial escalation is to be terminated and the subject will receive no further OIT, even if symptoms are assessed to be mild.

In the event of moderate symptoms occurring during the initial escalation, the initial escalation is to be terminated and the subject will receive no further OIT, regardless of whether treatment is instituted or what type of treatment is instituted. The only exception to this is if the occurrence of moderate symptoms is restricted to the 6 mg dose. In this case, and this case only, may testing be attempted the following day (Day 2 or Day 3) at a reduced dose (3 mg).

If the initial escalation is completed with no symptoms or only mild symptoms, subjects should have, at a minimum, a 2-h post-protocol observation period before continuing in the study. If the subject experiences moderate to severe symptoms, the observation period is to be at least 4 h, and up to 24 h (in an appropriate facility), based on the nature and severity of the symptoms and the treatment regimen required to stabilize the subject's condition.

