3.2 Treatment period

The treatment build-up phase will start with an initial escalation at the study center, followed by up-dosing for approximately 24 weeks. The treatments will be conducted in a double-blind fashion. An unblinded clinical site pharmacist will prepare the study medications at different doses according to each subject's treatment assignment. The subjects and the rest of the study personnel will be blinded to the treatment assignments.

After the initial escalation visit (comprising 2 or 3 days), subjects will report to the study center every 2 weeks to escalate their OIT dose, up to an expected daily dose of 300 mg/day of peanut protein in subjects able to tolerate the up-dosing. The dosing escalation schedule is described in detail in **Table 3-1** and **Table 3-2**.

Initial Days 1 to 3 (Visit 01) Escalation Schedule			
Dose #	Study Product Dose (mg peanut protein or placebo)	Cumulative Study Product Dose (mg peanut protein or placebo)	
1	0.5	0.5	
2	1.0	1.5	
3	1.5	3.0	
4	3.0	6.0	
5	6.0	12	
Doses will be delivered at 20 to 30 minute intervals.			
Subjects who are unable to tolerate a dose of 3.0 mg at the end of Day 1 will be considered an initial day escalation failure.			
All subjects who tolerate a dose of at least 3 mg on Day 1 will return on Day 2 to receive their maximum tolerated dose (3 mg or 6 mg) under direct observation.			
Subjects with either no symptoms or mild symptoms on Day 2 at either 3 mg or 6 mg may start daily dosing at their highest tolerated level, and will not be required to return for Day 3.			
Subjects who experience moderate or severe symptoms after receiving a 6 mg dose on Day 2 will return on Day 3 to receive the next lower dose (3 mg) under direct observation.			

Table 3-1.Initial Dosing Schedule for Peanut OIT

Subjects with moderate or severe symptoms at 3 mg on either Day 2 or Day 3 will be considered escalation failures.

Future dose escalations will occur every 2 weeks with the initial dose increase administered in the Clinical Research Center.

Table 3-2.Escalation Dosing Schedule for Peanut OIT

Escalation Dosing			
Dose #	Study Product Dose (mg peanut protein/day or placebo)	Interval (weeks)	% Increase
6	12	2	
7	20	2	67%
8	40	2	100%
9	80	2	100%
10	120	2	50%
11	160	2	33%
12	200	2	25%
13	240	2	20%
14	300	2	25%
Capsules are to be opened, content	s sprinkled over an age-appropriate food, and	mixed thoroughly.	-

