## 3.2.2 Treatment Period (Visits 01, 02 and Up-dosing Visits)

The treatment up-dosing phase will start with an initial escalation (Visit 01) at the study center, followed by up-dosing for approximately 24 weeks, conducted in a double-blind fashion. Up-dosing will continue until the subject reaches a steady dose of 300 mg/day, is unable to continue escalation due to symptoms, or withdraws from the study. If a subject does not require any dose reductions during the up-dosing phase, the target maintenance dose of 300 mg/day will be reached in either approximately 18 or 20 weeks, depending on whether up-dosing was started at 6.0 or 3.0 mg/day, respectively. Once achieved, the target dose of 300 mg/day is to be maintained for 2 weeks, for a total of approximately 20 or 22 weeks of dosing after the initial escalation visit. If, however, a subject does require dose reductions during the up-dosing phase, the total duration of dosing after Visit 01 may be extended up to an additional 12 weeks, for a total duration of up to 34 weeks.

During Visit 01 (comprising 2 or 3 days), doses will be delivered at 20 to 30 minute intervals, as described in Table 3.2. Subjects who are unable to tolerate a dose of 3.0 mg at the end of Day 1 will be considered an initial day escalation failure. All subjects who tolerate a dose of at least 3.0 mg on Day 1 will return on Day 2 to receive their MTD (3 mg or 6 mg) under direct observation. Subjects with either no symptoms or mild symptoms on Day 2 at either 3 mg or 6 mg may start daily dosing at their highest tolerated level, and will not be required to return for Day 3.

Subjects who experience moderate or severe symptoms after receiving a 6 mg dose on Day 2 will return on Day 3 to receive the next lower dose (3 mg) under direct observation. If the 3 mg dose is tolerated, subjects return home on that dose for 2 weeks until the next escalation. Subjects with moderate or severe symptoms at 3 mg on either Day 2 or Day 3 will be considered escalation failures.

Future dose escalations will occur every 2 weeks with the initial dose increase administered in the Clinical Research Center.

Initial Days 1 to 3 (Visit 01) Escalation Schedule					
		Cumulative Study			
	Study Product Dose	Product Dose			
Dose #	(mg peanut protein	(mg peanut protein			
	or placebo)	or placebo			
1	0.5	0.5			
2	1.0	1.5			
3	1.5	3.0			
4	3.0	6.0			
5	6.0	12.0			

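### Protocol Table 3-1, its synopsis copy and SAP 3.2.2 re-dose Visit 01 subjects whom Protocol 6.8.1 stops: chiefly severe reactors to 6 mg on Day 2, and less clearly mild reactors who needed a second drug

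*Protocol*

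**What the plan says.** **Schedule text.** Protocol Table 3-1 (Section 3.2), repeated in the synopsis, has three relevant lines:

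- Day 1: "All subjects who tolerate a dose of at least 3 mg on Day 1 will return on Day 2". SAP 3.2.2 says the same: "All subjects who tolerate a dose of at least 3.0 mg on Day 1 will return on Day 2".
- Day 2, mild: "Subjects with either no symptoms or mild symptoms on Day 2 at either 3 mg or 6 mg may start daily dosing", with no Day 3 visit required. SAP 3.2.2 has the same sentence.
- Day 2, moderate or severe at 6 mg: "Subjects who experience moderate or severe symptoms after receiving a 6 mg dose on Day 2 will return on Day 3", to be given 3 mg under observation. SAP 3.2.2 has this sentence too.

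None of these lines mentions the medication given for the reaction, and none refers to Section 6.8.1.

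**Stop rules.** Protocol 6.8.1 treats severe symptoms in initial escalation without exception: dosing ends whatever the dose, and the subject is an escalation failure. Its summary adds a medication stop. If an antihistamine alone is not enough and a second drug is needed, or if antihistamine doses are repeated beyond what the summary allows, "the initial escalation is to be terminated and the subject will receive no further OIT, even if symptoms are assessed to be mild". For moderate symptoms 6.8.1 also ends treatment, with one carve-out: "The only exception to this is if the occurrence of moderate symptoms is restricted to the 6 mg dose". In that case 3 mg may be tried the next day.

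**Section 6.4.1** lies between the two. Its introductory text and its Day 3 paragraph send only moderate reactors to Day 3. Its Day 2 line for 6 mg, however, sends anyone who did not tolerate the dose to Day 3 for 3 mg, and does not exclude severe reactions.

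**The concern.** A site working from Table 3-1 would give study product again to a subject whom 6.8.1 says must stop. In the severe case, that means 3 mg of possible allergen the day after a reaction that 6.8.1 illustrates with laryngeal edema, wheezing with dyspnea, altered mental status or hypotension. In the mild case, it means a return visit on Day 2, or the start of daily home dosing, for a subject who has just needed two drugs. Subjects may be as young as 4, and about 8 sites take part, so the same reaction could be handled differently depending on which section a site follows. The stake is participant safety and uniform conduct. The endpoint definition is not in question.

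**Working it through.** There is no figure in the plan to reproduce. The check sets the rules side by side for each type of Visit 01 reaction.

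| Reaction | Table 3-1, synopsis copy, SAP 3.2.2 | Protocol 6.4.1 | Protocol 6.8.1 |
|---|---|---|---|
| Severe, 6 mg, Day 2 | 3 mg on Day 3 | Day 3 paragraph: moderate only. Day 2 line: step down if not tolerated, severe not excluded | Stop at any dose; escalation failure |
| Mild, 6 mg, Day 1, second drug needed | Return on Day 2 | Return on Day 2 | No further OIT |
| Mild, 3 mg or 6 mg, Day 2, second drug needed | May start daily dosing | Home on that dose if tolerated | No further OIT |
| Moderate, confined to 6 mg | 3 mg the next day | 3 mg the next day | 3 mg the next day |

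**Row 1** is a direct contradiction. One text requires a further dose and the other forbids it. It does not depend on how 6.8.1 is parsed or on what Figure 6-1 shows, because no figure can make those two sentences agree.

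**Rows 2 and 3** are a gap. The Day 1 line is mandatory and covers all who tolerated 3 mg. A subject who reacts at 6 mg on Day 1 has normally tolerated 3 mg already, so the line applies. The Day 2 line is permissive. Neither says that it yields to the medication stop.

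**Row 4** agrees throughout.

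**Effect on the primary endpoint.** Under SAP 7.3 and Tables 7.1 and 7.2, a subject without an Exit DBPCFC is a non-responder, apart from documented ad libitum peanut consumption. The rule therefore changes a subject's dosing path, and changes the outcome only if that subject would otherwise have passed the Exit DBPCFC.

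- Arm size: about 50 subjects randomized 1:1, so 50 / 2 = 25.
- One subject: 1 / 25 = 4.0 percentage points at most.
- Loose scale for row 1: Protocol 1.6.1 expects fewer than 1% of subjects to have severe symptoms at some point in dosing. 0.01 × 25 = 0.25, so fewer than 0.25 subjects are expected in the active arm over all dosing, and fewer still at 6 mg on Day 2.
- Rows 2 and 3: the documents give no usable rate.

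**The case against.** **The process algorithm is Figure 6-1, which is not in the supplied text.** Section 6.8.1 points to it, and Section 3.2 says tolerability is monitored as the figures illustrate. It may well settle the mild two-drug case. It cannot repair the severe line, where the written sentences would still disagree.

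**Table 3-1 is a schedule and defers to Section 6.** The synopsis sends the reader to Sections 3 and 6 for therapy details, and SAP 1 sends the reader to the protocol for study conduct. So SAP 3.2.2 is a description and the protocol governs; that part stands. But the synopsis names both sections without ranking them, and Table 3-1 sits in Section 3.

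**The mild rules are cumulative.** A permission to start daily dosing does not override an explicit stop. For mild symptoms 6.8.1 offers only advancing or an antihistamine, and it ties added epinephrine or a beta-agonist to ending escalation. This is a fair reading and probably the intended one, which is why this part is the lesser point.

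**Re-dosing after a severe reaction may be intended.** In build-up, Section 6.8.2 lets the physician bring a severe reactor back at a reduced dose. But 6.8.1 is specific to Visit 01 and stops severe reactors outright, and the Day 3 paragraph of 6.4.1 names moderate reactors only. Table 3-1 is the outlier.

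**Safeguards exist.** The Medical Monitor is always available, investigator judgment applies, and Section 4.3.1 allows termination for severe symptoms. These reduce the risk but do not say which rule prevails.

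**A stronger reading does not hold.** A reader might infer that the medication stop also contradicts the step-down for moderate reactions at 6 mg ("If moderate symptoms occur only at the 6 mg dose") when two drugs were needed. The medication paragraph follows on from a sentence about mild symptoms. The next paragraph settles moderate reactions whatever the treatment, with 6 mg as a deliberate exception. That a mild two-drug reactor stops while a moderate one may step down is odd, but it is not a contradiction.

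**Conclusion.** The point holds in two parts of unequal weight. The severe Day 2 line in Table 3-1, the synopsis and SAP 3.2.2 directly contradicts 6.8.1 on a safety rule. The missing exception for mild reactions needing a second drug is a gap that a careful reader can bridge, but the text does not bridge it, and Figure 6-1 may or may not do so.

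The size is small. The number of subjects affected is not given and may be zero. Each subject stopped costs an arm of about 25 at most 4 points, and only if that subject would otherwise have passed the Exit DBPCFC. A reader might be tempted to scale this from the 2 epinephrine doses given during dosing among 39 active cases (Protocol 1.2) or from the 15% expected to have moderate symptoms (Protocol 1.6.1). Both cover all dosing and neither informs this step.

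A reader might also infer a threat to the efficacy conclusion. The documents do not support that. Responder classification is unambiguous, Visit 01 is blinded, the same rule applies to both arms, and a subject stopped early counts as a non-responder. In the CPNA arm, stopping can only lower the response rate. There is no false-positive risk.

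**What to change.** 1. In Table 3-1, its synopsis copy and SAP 3.2.2, delete *or severe* from the line that sends 6 mg Day 2 reactors to Day 3. Keep those words in the separate line that makes moderate or severe reactors at 3 mg escalation failures.
2. In the same three places, and in the 6.4.1 Day 2 line, add: *unless stopped under 6.8.1 (severe symptoms at any dose, or mild symptoms needing a second medication)*. The 6.8.1 summary also names multiple antihistamine doses, so list that trigger too if the parenthesis is meant to be complete.
3. Check that Figure 6-1 shows the same order of rules.
4. Leave the moderate-only 6 mg exception in 6.8.1 as written. Extending the medication stop to moderate 6 mg reactions would be a new clinical rule.

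The cost is a wording change in the protocol and SAP plus a memo to sites, with no added procedures or subjects. The downside is that an occasional subject becomes a Visit 01 escalation failure and an ITT non-responder, at most 4 points in that subject's arm.
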